### **Baseline assessment**

Data was collected for each participant regarding socio-demographic variables (age, sex, feeding practices), skin color, nature and duration of presenting symptoms. All children were examined for vital signs (temperature, heart rate, respiratory rate, blood pressure, oxygen saturation), pallor, cyanosis, nasal flaring, grunt, and mental status. Pa O2/FIO2 was measured and serum creatinine, C reactive protein, platelet count and serum bilirubin laboratory tests were done. SOFA score was assessed for severe pneumonia cases.

### **Intervention**

All children were treated with antibiotics according to WHO classification and treatment of childhood pneumonia at health facilities 2012 [18], at enrollment after obtaining consent from parents and completing the baseline assessment, children were given a single injection of one ml of 100.000 IU of vitamin D3 (Cholecalciferol), vitamin D3 obtained from 2 ml vials containing 200,000 IU each (Devarol- S- 200.000 I.U. produced by Memphis for Pharmaceutical and Chemical Industries) and stored in manufacturer's recommended conditions in a dry, cool environment for 1–16 weeks (depending on the date of recruitment) or placebo which is 1 ml saline injection. Syringes were labeled with a unique ID number and given by the blinded doctors choosing the next syringe with a randomization code. (only office secretary aware of randomization codes).

### **Hospital follow-up**

Children were monitored with recording data every eight hours for respiratory rate, chest indrawing, oxygen saturation, auscultation findings, fever, feeding, cyanosis, and mental status. The child was discharged when fever and fast breathing were absent for 2 consecutive days.

### **Outcomes assessment**

Outcomes were assessed 7 days after vitamin D injection, the first day whereas vitamin D reaches its maximum level in the blood [19] to guarantee the assessment of all participants before their

discharge. The primary outcome variables were changed in serum level of 25(OH)D, PaO2/FIO2, serum creatinine, C reactive protein, and serum bilirubin levels and platelets count. Also, the SOFA score for severe cases. The secondary outcomes included the fate of the cases (improvement or death) and the duration between enrolment and hospital discharge for improved cases.

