In Egypt 2010, a case-control study conducted on children aged 2 to 5 years to examine the impact of vitamin D deficiency on the susceptibility of pneumonia. The study illustrated that Vitamin D deficiency is associated with a higher incidence and more severe pneumonia(11).

Hashemian H., et al 2017, advocated providing children(particularly suffering from pneumonia) with adequate amounts of vitamin D supplements(12).

Nevertheless, few studies have been conducted to evaluate the impact of vitamin D supplementation on the outcome of pneumonic infants.

Thus, we urge to conduct a randomized controlled trial (RCT) in Abou ElReesh tertiary Pediatric hospital, to evaluate the effects of vitamin D3 supplementation to children with pneumonia. We postulated that supplementation of 100 000 IU of vitamin D3 (Cholecalciferol) will reduce the duration of illness in those children and improve their outcome.

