### **Subjects and Methods:**

#### **Study design and study setting**

The current study is a randomized, double-blinded placebo-controlled trial (RCT) that was conducted in Cairo University Abou ElReesh Children hospital, which is a university-affiliated teaching hospital in Egypt, to evaluate the effect of vitamin D3 supplementation on the outcome of treatment of children with pneumonia. Pneumonia cases were recruited from two of the hospital general pediatric departments and the four pediatric intensive care units (PICUs) of the hospital.

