#### **Sample Size and study population**

To detect a 20% difference in the mean duration of pneumonia between the vitamin D arm and control arm [5 days vs. 6 days (SD 2)] allowing Type I error of 5% and Type II error of 10%, 86 per group (172 total) is the minimum number to be recruited [13]. After allowing for 10% for nonresponse or loss for follow-up and 25% for exclusion of children diagnosed with sufficient or toxic level of vitamin D after vitamin D testing (Box 1) according to prevalence of vitamin deficiency in a pediatric hospital of eastern India [14], 233 was the minimum number to start with. Mild and moderate pneumonia cases were recruited from two of the hospital general pediatric departments chosen by simple random sample from a total of six hospital departments while severe pneumonia cases were recruited from the four PICUs of the hospital.

All children (259 children) between 1 month and 12 years of age admitted to the selected departments during the period from 9th September 2019 to 15th December 2019 and diagnosed clinically with pneumonia according to World Health Organization criteria of severity [15] (Box 2) were screened for the inclusion criteria. Children who had clinical signs of rickets (2 children), severe illnesses (meningitis, heart or renal disorders, measles, severe malnutrition, endocrine dysfunction, hypercalcemia, hyperthyroidism, and suspected tuberculosis) (4 children) or were known to have received high-dose vitamin D treatment in the past 3 months (3 children) were excluded from the study. Children with sufficient (52 children) or toxic (7 children) levels of vitamin D were also excluded.

Thus, 191 child (93 in the intervention arm and 98 in the control arm) who had pneumonia with insufficient or deficient level of vitamin D and their parents consented to participate were actually enrolled in the study, completed the baseline and the outcome assessments and continued the daily clinical follow up till their discharge (improvement or death) from the hospital.

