#### **Statistical analysis:**

Patients' percent change of Vitamin D (25 (OH)2D) was calculated to quantify the change levels before and after vitamin D3 (Cholecalciferol) administration through the equation:

Pediatric, Blood Vitamin D level (BVD) %change =

$$[(\text{BVD after} - \text{BVD before}) \div \text{BVD before}] \times 100$$

Collected data were entered and analyzed using the Statistical Package for Social Science Software (SPSS) program, version 21.0 IBM. Tests of normality of data (like Shapero-Wilk test) revealed that data isn't normally distributed. That's why non-parametric tests like MannWhitney and Kruskal-Wallis tests were used in univariable comparisons to quantify the associations of continuous variables. Data were summarized using the median and interquartile range for quantitative variables. Spearman correlation test was used to detect the relationship between continuous variables. P values below 0.05 were considered statistically significant. A multivariate Cox regression analysis model was conducted to explore the independent effect of vitamin D3 supplementation on the overall survival of pneumonic children.

Given the short period of the study follow-up and single intervention, there was no stopping rule or interim analyses.

All children randomized were included in the analysis on an intention-to-treat basis unless the outcome measures were missing (n = 0) or reported to have recovered or lost within 24 h (n = 0). Meantime to recovery for the episode of pneumonia at recruitment was compared for the vitamin D group and control group. Kaplan-Meier plots and log-rank tests were used to compare the time to recover from the index episode of pneumonia between the vitamin D and placebo groups.

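### The stated 90% power belongs to mean duration of pneumonia, not to any of the seven listed primary outcomes, and the document gives no lead outcome, error control or success rule for those seven

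*Combined protocol and SAP*

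**What the plan says.** The Introduction postulates that vitamin D3 "will reduce the duration of illness in those children and improve their outcome". Study design and study setting gives a broader aim, "to evaluate the effect of vitamin D3 supplementation on the outcome of treatment of children with pneumonia".

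Sample Size and study population sizes the trial "To detect a 20% difference in the mean duration of pneumonia between the vitamin D arm and control arm": 5 versus 6 days, SD 2, Type I error 5%, Type II error 10%, 86 per group and 172 in total. It reports 191 children enrolled, 93 and 98 per arm.

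Outcomes assessment then ranks the outcomes differently:

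- **Primary:** "The primary outcome variables were changed in serum level of 25(OH)D", followed by PaO2/FiO2, creatinine, C reactive protein, bilirubin and platelet count, and then "Also, the SOFA score for severe cases". That makes seven.
- **Secondary:** "The secondary outcomes included the fate of the cases (improvement or death) and the duration between enrolment and hospital discharge for improved cases".

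Statistical analysis gives one significance criterion: "P values below 0.05 were considered statistically significant". It defines a change measure (percent change) for 25(OH)D only. It names Mann-Whitney among the tests for continuous variables because the data were not normal. It also says "Meantime to recovery for the episode of pneumonia at recruitment was compared for the vitamin D group and control group", and adds Kaplan-Meier plots and log-rank tests for time to recovery, on an intention-to-treat basis.

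**The concern.** The outcome that justified the number of children is not among those declared primary. None of the seven primaries has a stated effect size, SD or power, so a null result on one of them cannot be read against a planned power, and the 10% Type II error cannot be quoted for it.

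The 5% Type I error holds per comparison only. Without a lead outcome, an order of testing or a definition of success, one significant marker out of several could be presented as a positive primary result. So could the 25(OH)D result alone. 25(OH)D is a metabolite of the injected cholecalciferol, and the children were selected for low levels, so a rise shows that the injection was taken up. It does not show that pneumonia improved.

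**Working it through.** **1. Reproduce the stated sample size.** Inputs from Sample Size and study population: difference 1 day, SD 2, Type I error 5%, power 90%. Sidedness is not stated; two-sided is the reading that fits.

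- Normal approximation: n per arm = 2 × (1.960 + 1.282)² × 2² / 1² = 84.06, so 85.
- t-test: n = 85.03, rounded up to 86. Power is 89.99% at 85 per arm and 90.3% at 86.
- Check on the reading: a one-sided test would need 69 per arm, and 80% power would need 63.

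The stated 86 per group is correct for a two-sided comparison of mean duration. The fault is not in the arithmetic but in which outcome it serves.

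**2. Compare the outcome sized with the outcomes listed.**

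| Section | Duration outcome | Rank |
|---|---|---|
| Introduction | duration of illness | first part of the hypothesis |
| Sample Size | mean duration of pneumonia | basis of the 90% power |
| Outcomes assessment | enrolment to discharge, improved cases only | secondary |
| Statistical analysis | time to recovery, all randomised children | not ranked |

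The wordings differ and the document never equates them. Enrolment to discharge is the nearest listed outcome to the one sized.

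**3. False-positive risk without a success rule.** Set 25(OH)D aside as a measure of uptake, which leaves six primaries. Assume that all six are null and that any one p<0.05 counts as success.

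- Independent: 1 − 0.95⁶ = 26.5%.
- Equicorrelated normal test statistics, by numerical integration: 25.4% at correlation 0.2, 20.7% at 0.5, 13.9% at 0.8.
- SOFA is measured in severe cases only. If that is a fraction f of children, its correlation with the other five test statistics becomes ρ√f. With f between 25% and 50% (assumed), simulation gives about 26%, 22% and 16% for ρ = 0.2, 0.5 and 0.8.

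**4. Power for the markers.** The document gives no effect size, so 0.5 SD is assumed, and the number of severe cases is not given. Two-sided t-test at 0.05, and at Holm's first step of 0.05/6 = 0.0083:

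| Outcome | Children per arm | 0.05 | 0.0083 |
|---|---|---|---|
| Marker in all children | 93/98 | 93% | 78% |
| SOFA, 25% severe | 23/24 | 39% | 16% |
| SOFA, 50% severe | 46/49 | 67% | 40% |
| SOFA, 75% severe | 70/73 | 84% | 62% |

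Mann-Whitney under normality (relative efficiency 3/π) gives about 92% and 76% in the first row. At 0.4 SD with 93/98, the t-test gives 78.5% and 54%.

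**5. What Holm achieves.** With all six null, the chance of any false positive is 4.9% if independent, and 4.8%, 4.1% and 2.8% at correlations 0.2, 0.5 and 0.8.

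**The case against.** Several primary outcomes can be legitimate, and physiological markers fit the broader aim. That stands: listing them is not the error.

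The 26.5% rests on an any-one rule that the document does not state. If all seven had to succeed, error would not be inflated, although power would fall. This also stands, which is why the figure is conditional. The document does not say which rule applies.

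The text is a past-tense account and refers to a protocol approved in July 2019. The claim can therefore only be that this document states no error control, not that none was ever specified.

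Holm applied after unblinding does not restore confirmatory status, and for a completed trial a null marker can be read from its confidence interval. Both points stand. The adjustment also needs one defined contrast per marker, which is missing for six of the seven.

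A reader might infer that the trial is underpowered. The document does not support that: 191 enrolled exceeds 172, and a marker measured in all children would have about 93% power at an assumed 0.5 SD. SOFA depends on an unreported number. Severe cases came from four intensive care units and milder ones from two wards, so a severe majority is possible.

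A reader might also infer that mean time to recovery has no applicable test. The general Mann-Whitney statement could cover it. The narrower point is that a comparison of means was sized, while the methods named are rank-based.

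**Conclusion.** The concern holds and needs correction. By the document's own text, the planned 90% power applies to none of the seven listed primaries, and no lead outcome, hierarchy, error control or success rule is stated for them. This part rests on no assumption.

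The size of the false-positive risk does rest on assumptions: six null markers, an any-one reading, and a correlation that the document does not give. On those terms it lies between about 14% (correlation 0.8) and 26.5% (independence), against a nominal 5%.

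A reader might conclude that duration was the true primary and should simply be reinstated. The document does not establish that. Unblinding has taken place, so promoting duration without an earlier record would itself be an outcome switch.

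**What to change.** 1. In Sample Size and study population, state that the 90% power refers to a comparison of mean duration and to none of the listed primaries.
2. Keep the recorded primary list, but interpret 25(OH)D as evidence of uptake and not of efficacy.
3. For the other six, state one contrast per marker, for example the between-arm difference in absolute change from baseline to day 7 by Mann-Whitney. Take it from a record made before unblinding if one exists; otherwise disclose the choice as post hoc. Apply Holm across the six (smallest p against 0.05/6 = 0.0083, next against 0.05/5 = 0.01, and so on), labelled post hoc unless pre-specified. Report estimates with confidence intervals, and call the markers exploratory unless a prior record supports confirmatory status.
4. Report time to recovery in all randomised children beside the primaries, as the analysis closest to the hypothesis. Count children who die as not recovered: treat death as a competing event, or censor at the end of follow-up rather than at death. Note that the log-rank and Mann-Whitney tests are not the comparison of means that was sized.
5. Name duration as the single primary only if a record made before unblinding, such as the protocol approved in July 2019, supports it. Otherwise disclose any re-ordering as post hoc.

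**Cost.** No extra children or data are needed. The work is wording in three sections, six defined contrasts with adjusted p-values and intervals, the handling of deaths, and a check of the July 2019 protocol. The price is power: a smallest marker p-value between 0.0083 and 0.05 would no longer count as significant. The losses at Holm's first step are in the power table above, and SOFA would be hit hardest if severe cases are few.

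### Change in serum 25(OH)D, a marker of exposure to the injected vitamin D3, is listed first among the primary outcomes, but a significant result on it would not be evidence of benefit in pneumonia

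*Combined protocol and SAP*

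**What the plan says.** The Introduction sets the hypothesis: vitamin D3 "will reduce the duration of illness in those children and improve their outcome". Study design and study setting gives the aim as its effect on the outcome of treatment in children with pneumonia.

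Outcomes assessment then says: "The primary outcome variables were changed in serum level of 25(OH)D", and continues with PaO2/FiO2, creatinine, C-reactive protein, bilirubin and platelets, plus SOFA in severe cases. Fate (improvement or death) and time from enrolment to discharge are secondary. Measurement is on day 7, described as "the first day whereas vitamin D reaches its maximum level in the blood"; the same sentence adds a second reason, that all children could be assessed before discharge.

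Under Intervention, one arm receives a single injection of 100,000 IU cholecalciferol and the other 1 ml of saline. Vitamin D testing describes an assay of total 25OH vitamin D (D2 and D3). Children with sufficient or toxic levels were excluded (Sample Size and study population).

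Statistical analysis defines a percent change in the vitamin D level, names Mann-Whitney among the tests for continuous variables, and gives one significance convention: "P values below 0.05 were considered statistically significant". The documents nowhere call 25(OH)D a check of exposure, rank the primaries, or limit what a significant 25(OH)D result may support.

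**The concern.** A primary outcome should answer the trial's question. Change in 25(OH)D answers a different one: whether the injected vitamin was delivered, absorbed and converted. Three design features make a difference between the arms likely whatever happens to the lungs: vitamin D3 is compared with saline, only children with low levels take part, and the level is read at its expected peak.

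A significant result on this outcome therefore cannot distinguish vitamin D3 helping children with pneumonia from vitamin D3 raising vitamin D levels. Yet it carries the rank of a primary outcome, above recovery time and death. Adjusting for several primaries would not cure this, because the null hypothesis for 25(OH)D is expected to be false by design.

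**Working it through.** **1. The plan's own sample size.** It is based on duration of pneumonia, "5 days vs. 6 days (SD 2", with "allowing Type I error of 5% and Type II error of 10%, 86 per group (172 total) is the minimum number to be recruited". For two means, n per arm = 2(z₀.₉₇₅ + z₀.₉₀)² × (SD/difference)² = 2 × (1.960 + 1.282)² × (2/1)² ≈ 84.1, so 85. The t-based calculation gives 85.03, which rounds up to 86. The stated 86 per group is reproduced with a two-sided test; a one-sided test gives 69. The sizing rests on duration, and no 25(OH)D effect enters it.

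**2. Power on 25(OH)D at the enrolled numbers.** The plan reports "191 child (93 in the intervention arm and 98 in the control arm". The documents give no expected rise or SD for 25(OH)D, so a range of standardised differences d is assumed. Power = Φ(d/√(1/93 + 1/98) − 1.960), where √(1/93 + 1/98) = 0.1448. For d = 0.5: 0.5/0.1448 − 1.960 = 1.494, and Φ(1.494) = 93.2%.

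| Assumed d (SD units) | Power, normal formula | Mann-Whitney simulation (4,000 runs, normal data) |
|---|---|---|
| 0.3 | 54% | 53% |
| 0.4 | 79% | not run |
| 0.5 | 93% | 92% |
| 0.6 | 98.6% | 98.5% |
| 0.75 | 99.9% | 99.8% |
| 1.0 | about 100% | 100% |

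Solving for d, 90% power needs (1.960 + 1.282) × 0.1448 = 0.47 SD, and 99% power needs (1.960 + 2.326) × 0.1448 = 0.62 SD.

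**3. The same in ng/mL.** All effect inputs here are assumptions: baseline mean 17 and SD 6, kept within 4 to 29.9; SD of within-child change 5 or 8; a rise in the vitamin D arm only; no clinical effect. Percent change as the plan defines it was compared by Mann-Whitney in 3,000 simulated trials per scenario, with 86 per arm.

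| Mean rise (ng/mL) | P < 0.05, change SD 5 | P < 0.05, change SD 8 |
|---|---|---|
| 0 | 4.5% | 4.6% |
| 2 | 69% | 34% |
| 3 | 96% | 63% |
| 5 | 100% | 97% |
| 10 | 100% | 100% |

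With 93 and 98 children, a rise of 3 gives 97% or 69%, and a rise of 5 gives 100% or 98%. Dividing 0.05 by the seven primaries (six variables plus SOFA) still leaves a 5 ng/mL rise significant in about 100% or 88% of trials at 86 per arm. This is why a multiplicity adjustment does not address the point.

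**The case against.** **The plan never says that one significant primary makes the trial positive.** This stands. A reader might infer that the plan is bound to return a positive trial even if vitamin D3 does nothing for pneumonia. The documents do not support that: they define no success rule, the 0.05 threshold is a convention for each test, and recovery time and survival have their own planned analyses (Kaplan-Meier, log-rank, Cox). The point is limited to what a result on this one primary can mean.

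**The percentages are not false-positive rates.** This stands too. It is tempting to set 93% or 98% against the nominal 5%. But if the injection raises 25(OH)D, rejecting that outcome's null is a true positive. The complaint is about relevance, not type I error.

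**25(OH)D is not the injected substance.** Correct: cholecalciferol is injected and total 25OH vitamin D is assayed. It is a direct marker of exposure, and the reasoning needs no more than that.

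**The size is assumed, and some of the analysis is inferred.** Also correct. With a small or very variable rise, significance is far from assured (34% for 2 ng/mL with SD 8). The plan does not explicitly say that percent change is compared between arms by Mann-Whitney, although that is the natural reading. Day 7 was also chosen partly for convenience before discharge.

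**Correcting a low level is a reasonable proximal aim in children selected for low levels.** That justifies measuring and reporting it. It does not make it an answer to the hypothesis in the Introduction, which concerns duration of illness and outcome.

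**Conclusion.** The point holds. An exposure marker is listed first among the primaries, its movement is anticipated by the design, and nothing in the documents limits what a significant result on it may support. Such a result would confirm exposure and is not evidence of benefit in pneumonia.

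How likely a significant result is depends on a rise and an SD that the documents do not give. At the enrolled numbers a difference of about 0.47 SD is enough for 90% power, while below about 0.4 SD the result is not assured. These figures rest on a two-sided 0.05 test between the arms and on approximately normal data. The logical point, that the outcome does not measure pneumonia, does not depend on them.

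**What to change.** - **Outcomes assessment:** move change in serum 25(OH)D out of the primary outcomes and list it as a biochemical check of delivery and absorption.
- **Statistical analysis:** state that 25(OH)D is reported by arm as confirmation of exposure, and that no conclusion about benefit in pneumonia rests on it.
- **Disclosure:** enrolment is complete, and the analysis section already reports normality results. The reclassification must therefore be declared openly as a post hoc change, with the outcome's previous primary status shown. If the sponsor prefers to leave the outcome list untouched, the interpretive statement should be added at minimum.

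The cost is a few sentences and the disclosure; no new data or patients are needed, and the 25(OH)D results are still reported. The trial gives up one primary outcome that was likely to be significant.

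Two separate problems remain: multiplicity among the five or six other primaries, and the secondary status of duration, the outcome on which the trial was sized. If those other primaries were all null and independent, the chance of at least one P < 0.05 would be 1 − 0.95⁵ = 22.6% or, with SOFA, 1 − 0.95⁶ = 26.5%.
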